Developments at the Cleveland Clinic have allowed our surgeons to use pre-operative planning software for simulation of the surgical plan to select the optimal implant from an inventory of FDA approved and commercial available implants and the optimal location of that implant within the bone. An ongoing clinical trial, IRB #12-997, is examining the use of the preoperative plan in correlation with an intelligent reusable instrument (IRI) to transfer the surgical plan information from the surgical model to the surgical site. The IRI is a tool provided to the surgeon with plastic adjustable legs to be adjusted onto to a sterile model of the surgical site having within the model the information needed from the pre-operative computer simulation of the surgical procedure. In the proposed new clinical trial we propose to create in the operating room a mold of the bone model that we call a Real Time Instrument (RTI) that the surgeon can place onto the patient glenoid bone to transfer the guide pin in the bone in a location defined to be optimal for the placement of the glenoid implant. Using the RTI, the surgeon can directly

determine the best features of both the patient's bone and the feature on the bone model that is within the surgical exposure to capture information within the RTI mold. The proof of the RTI concept for glenoid pin placement has been demonstrated in pre-clinical sawbone models and surgical trainers that simulate the surgical environment.

In a pre-clinical sawbones trial, we demonstrated a significant improvement in the accuracy of glenoid pin placement between Real Time Instrumentation and the standard of care instruments. Two surgeons were asked to place a guide pin in nine different pathologic models utilizing the two surgical techniques. The sawbone models were housed in our novel shoulder surgical trainer to simulate operative exposure. Standard of care with pre-surgical CT (n=36) and RTI (n=36) were performed to assess deviation from the preoperative plan. (Figure 3)

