We are proposing the first in man use of this technology for placement of the glenoid component in anatomic total shoulder arthroplasty. We will use, as we have for our completed PSI clinical trial and currently active IRI study, post-operative 3D CT Scanning to precisely define the location of the implant as compared to pre-operative plan. We propose to compare the accuracy of implant placement using the RTI - SmartBone technology to the use of IRI and PSI groups as well as the two control groups from these trials. Specifically we are proposing a non-randomized clinical case series. Patients enrolled in this study will be operated on by surgeons involved in the pre-clinical trial and the ongoing IRI study. In all enrolled RTI cases the surgeon will have full control to define the optimal position of the guide pin and the final implant. The surgeon can default to standard of care technology in any case in which the RTI technology cannot be used or results in a guide pin position that in his view is not consistent with the pre-operative plan. Therefore the surgeon is in full control of all intraoperative decision making and execution of the procedure.

In the 60 patients treated in the PSI and IRI study there has not been the need to abort the use of the novel instrumentation, nor has there been a complication during or after surgery relating to the technology. Moreover the objective data of post-operative implant position has proven the PSI and IRI technology to be better than control groups. It is for these reasons that we do not propose to do a randomized clinical trial.

Measurement of Implant Position

Post operatively we will obtain a CT scan with metal artifact reduction technology within the first few weeks after surgery and will generally obtain this scan prior to discharge from the hospital. A second CT scan will be obtained at two years after surgery. We have used these methods of 3D CT imaging to determine implant position in several prior studies. We have defined the accuracy of these measurements using first generation techniques to be within 1 millimeter and 3 degrees. We anticipate that the accuracy of these second generation imaging techniques will be improved from our earlier work.

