To assess bone quality and its effect on glenoid component loosening, we will take trabecular bone samples from all patients. Humeral heads, which are normally discarded as standard of care medical waste will be kept and evaluated with mechanical testing. These bone samples will be assessed by micro CT to measure trabecular bone volume and connectivity as well as by mechanical testing. This data will be correlated with the trabecular bone volume of the glenoid defined by the pre-operative CT scans. In addition all bone quality measurements will be correlated with CT scan imaging of the glenoid at the time of surgery and at two year follow up.

Patient Enrollment

The proposed clinical study will enroll patients indicated for standard of care anatomic total shoulder arthroplasty. They will receive all pre-operative testing, intra-operative care including all implants and post-operative care that is standard of care and specific to the surgeon and patients decisions for care. The only change for the case series will be the type of surgical instruments used to place the glenoid guide pin, coring of the bone to obtain bone tissue, placement of the beads and post-operative CT scanning. In all cases the surgeon is able and allowed to use their own surgical judgment to place the guide pin, prepare the bone and place the desired implant. In all cases, the surgeon can use any and all of the standard instruments or guides provided by the implant manufacturer as the surgeon would use if the patient was not enrolled in the study. If the surgeon chooses not to use the RTI technique then this would be noted as a deviation in plan, the reasons recorded and the patient would be excluded from the study without post-operative imaging and their pre-operative and intra operative data would be

analyzed for the purpose of understanding the reasons for failure of the RTI technology to provide assistance for refinement of the technology.

Detailed Study Design:

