The study will enroll 20 patients directly into the RTI group. We will have two surgeons with experience in shoulder arthroplasty and the RTI and SmartBones technology. We will require a minimum of five patients from any one surgeon. All patients will have the standard of care indications for an anatomic total shoulder arthroplasty and will give informed consent for both the surgery and participation in this study. Consent and enrollment will be obtained by the surgeon during a routine office evaluation. All patients will get standard of care pre-operative x-rays and CT scan at least three weeks prior to surgery. Scan quality must meet study specific criteria and we expect that the scans will be performed at the Cleveland Clinic. The pre-operative CT scan will be placed within our pre-operative planning software (OrthoVis Cleveland Clinic). The surgeon will use this software to assess the glenoid bone pathology and select the optimal implant and placement of that implant.

Patients will have standard of care indications for primary anatomic arthroplasty and be able to get a pre-operative shoulder CT scan at the Cleveland Clinic or at an outside facility so long as the study includes the entire scapula and has 1mm or thinner sections. These parameters are required for accurate pre-operative planning as well as comparison with the post-operative CT scans. Standard of care pre- and post-operative x-rays (AP and axillary views) will also be obtained and can be performed at the Cleveland Clinic or acquired from another health care facility. In all patients the standard x-rays and CT images provided by the radiology department will be available to the surgeon before and during the surgery.

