Prior to implanting the glenoid component, three 1mm tantalum beads will be inserted into the backside pegs of the component. We have developed methods to place the beads in a manner that has been used by other investigators and validated in our own experience in 22 cases enrolled in the ongoing IRI clinical study. The desired implant will be placed into a holding device and using a drill guide, a 0.9 mm hole measuring 2 mm deep will be placed in each of the three peripheral pegs of the implant. A 1 mm tantalum bead (RSA biomedical, Umsa Sweden) supplied by the company will then be press fit into the component hole. The implant will then be placed in the glenoid, aligned with the previously drilled peg holes. As standard of care, these peg holes are cemented, thus locking the beads within the implant.

Using manufacturer (RSA biomedical, Umsa Sweden) provided beads and injector gun, four to five 1mm tantalum beads will be placed in the coracoid, acromion and glenoid. Exact placement of these beads is at the discretion of the surgeon. Patient anatomy and operative exposure will guide the surgeon to the best places to inject the beads; however the surgeon will not be confined to a specific amount of beads in a specific location. The beads just need to be spread out amongst the coracoid, acromion, and glenoid to establish reference points for the RSA imaging. Prior studies looking at shoulder joint kinematics and implant position have used this methodology of bead placement with successful study related outcomes. We have successfully placed bone beads in 22 patients currently treated in the ongoing IRI clinical study without any difficulty or adverse events during or after surgery.

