Clinical data collected pre and post-operative will be Passive and Active range of motion, manual muscle strength testing and shoulder functional scores, and co-morbidities all of which are standard of care. Post-operative data will be collected at two years (\pm 1 month) after surgery. We will collect at the time of surgery the implant used, the time for surgical care glenoid exposure to end of pin placement. The implant used, the surgical instruments used and any comments from the surgeon as to the ease of use and accuracy of the RTI instruments. Verbatim comments will be solicited and recorded by a research assistant attending all surgical procedures.

Pre-operative imaging data will include: Glenoid version and inclination, estimated pre morbid inclination, version and depth of glenoid bone loss using the glenoid vault model. Preferred implant type inclination and version.

Post-operative implant placement to desired location will be defined for location of the center peg of the implant in the SI, AP and ML dimension in millimeters and the trajectory of the center peg actual vs plan in version and inclination. The location of the implant in relation to the joint line as measured by the glenoid vault model will be measured in millimeters. Back side contact of the implant to the bone will be measured as a surface area in direct contact with the bone and any lucent lines around the implant pegs will be measured. Peg perforation and the location of the peg perforation will be recorded. The tantalum beads within each implant will be measured for translational or rotational movement.

Changes in implant position from post-operative CT scan 1 vs CT Scan 2 will be correlated with back side seating, implant type, medialization of the joint line and peg perforation and severity of the post-operative pathology.

Study data will be collected and managed using REDCap (Research Electronic Data Capture).

[Adverse Events and Data Monitoring Committee \(DMC\):](#)

A Data Monitoring Committee will not be used. Patient safety will be protected by following surgical standards of care. The IRB will be notified in writing of any adverse clinical event related to the use of the IRI or the standard instrumentation. Adverse events include excessive bleeding, infection, fracture nerve injury or need for revision surgery during the term of this study which is expected to be approximately 1 year from the time of surgery.

Consent:

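### The only adverse-event reporting rule names a device from another trial, omits the first-in-man RTI and the tantalum beads, and gives a 1-year study term against a two-year schedule

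*Combined protocol and SAP*

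**What the plan says.** The section headed Adverse Events and Data Monitoring Committee (DMC) states that there will be no DMC and that patients are protected by surgical standards of care. Its reporting rule is: "The IRB will be notified in writing of any adverse clinical event related to the use of the IRI or the standard instrumentation". It then lists the events that count (bleeding, infection, fracture, nerve injury, revision) and closes the list with "need for revision surgery during the term of this study which is expected to be approximately 1 year from the time of surgery".

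Other sections describe a different device and a longer follow-up:

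- **Device.** Glenoid Instrumentation and Pre-operative planning places the IRI, a tool with adjustable legs, in the ongoing trial IRB #12-997. It defines the RTI as a separate object, a mold made in the operating room, and says: "We are proposing the first in man use of this technology for placement of the glenoid component". Detailed Study Design says: "The study will enroll 20 patients directly into the RTI group".
- **Beads.** Detailed Study Design says "Prior to implanting the glenoid component, three 1mm tantalum beads will be inserted into the backside pegs of the component", and also "four to five 1mm tantalum beads will be placed in the coracoid, acromion and glenoid". Patient Enrollment lists what changes for the case series besides the pin-placement instruments: "coring of the bone to obtain bone tissue, placement of the beads and post-operative CT scanning".
- **Follow-up.** Measurement of Implant Position schedules a second CT at two years. Detailed Study Design schedules that CT, with RSA for those who had it originally, at 2 years ± 1 month. Data Sheets sets the same window for post-operative clinical data.

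**The concern.** The notification sentence reads as if carried over from the IRI protocol. It names an instrument to which no patient here is assigned, and it leaves out both the device being tried for the first time and the markers added for research. The study term in the same paragraph is about half of the follow-up scheduled elsewhere.

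With no DMC, this sentence tells site staff which events go to the IRB. If they follow it literally, three kinds of event can go unreported: those attributed to the cement mold, those attributed to the beads, and revisions in the second year. Revision matters particularly because the Overall Summary calls glenoid loosening the most common complication of the operation, and Outcome Measures plans to relate bone quality to loosening.

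The imaging measurements of placement and loosening do not depend on this rule. Neither do the sample size, the 5% significance level or the planned mixed-effects ANOVA.

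**Working it through.** **1. Which devices and procedures does the rule cover?**

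| Item | Used in this study? | Named in the rule? |
|---|---|---|
| IRI | No patient assigned; instrument of IRB #12-997 | Yes |
| Standard instruments | Yes, after the mold is removed, or if the surgeon reverts to them | Yes |
| RTI (SmartBone model and cement mold) | Yes, all 20 planned patients | No |
| Beads in the implant | Yes, 3 planned | No |
| Beads in bone | Yes, 4 to 5 planned | No |

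Nominal beads per patient: 3 + 4 = 7 to 3 + 5 = 8.

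**2. Could IRI be read to include RTI?** The Overall Summary says the RTI combines features of PSI with IRI technology. The protocol nevertheless keeps the terms apart. Outcome Measures lists the two as different technologies to be compared, and Statistical Methods makes them separate groups in the ANOVA. The label cannot be stretched to mean both in this one sentence.

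**3. Does another section fill the gap?** Patient Enrollment and Detailed Study Design have the reasons for RTI failure recorded and analyzed. Data Sheets has bead movement measured. These are data-collection steps, and neither is tied to IRB notification.

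**4. Stated term against scheduled follow-up.**

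- Stated term: about 12 months from surgery.
- Last scheduled assessment: 24 − 1 = 23 months to 24 + 1 = 25 months.
- Time outside the stated term: 23 − 12 = 11 months to 25 − 12 = 13 months.
- Share of follow-up inside the term: 12/25 = 48% to 12/23 = 52%.

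The 1-year figure cannot be reproduced from the protocol's own schedule, which gives 23 to 25 months per patient.

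**5. Event counts.** The documents give no event rate for the RTI, so no number of missed events is estimated. They report no adverse events from bead placement in 22 patients of the IRI study. Those patients did not receive the RTI, so this says nothing about the mold.

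**The case against.** Both mismatches are plain in the text. The case against concerns how much follows from them.

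- **The rule is not worded as exclusive.** It says which events will be notified and does not say that no others will be. The list of adverse events carries no device qualifier. In a protocol with one enrolled group, IRI is probably a slip for RTI, and staff may well report RTI events anyway. This is fair, and it means actual under-reporting is not established. It does not make the sentence correct.
- **Every RTI operation also uses standard instruments**, so many events would be notifiable regardless. This stands. The gap is events attributed to the mold or the beads alone. The figure of 20 patients counts those exposed to a device the rule does not name, not those outside all reporting.
- **The 1-year figure may be a misstated term rather than a cutoff**, or may qualify only revision. Either is possible. On the first reading the 11 to 13 months measure a textual conflict and no reporting time is lost. On the second, second-year revisions still fall outside the rule.
- **The bead count is nominal.** The surgeon is not held to a fixed number of bone beads. RSA is optional, and the protocol does not say whether patients without it receive bone beads. This is correct; 7 to 8 is the plan, not a guaranteed count or a measure of harm.
- **Bone coring is listed beside bead placement but left out of the proposed wording.** This is minor, because the Overall Summary and Bone Quality Measurements describe the samples as humeral head tissue that is normally discarded. It could be added in the same edit.
- **A deliberately shorter adverse-event window, stated as such, would also remove the contradiction.** This is true, but the present text describes the term of the study, not a separate window.

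**Conclusion.** The concern holds. The sole reporting rule in a first-in-man study without a DMC names a device that is not assigned here, and it omits the RTI used in all 20 planned patients and the nominal 7 to 8 beads in each. Its study term of about 12 months is inconsistent with the scheduled 23 to 25 months, a difference of 11 to 13 months or about half of follow-up.

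The two mismatches rest on the text and simple subtraction. The consequence, that some events need not be notified, assumes that staff apply the sentence as written. Events attributed to standard instruments remain covered, and expected counts of bead-related events may be low. This should be fixed as a matter of safety reporting; it is not a threat to the planned analysis.

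**What to change.** Make two edits in the adverse-event section:

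1. In the notification sentence, name the RTI (SmartBone model and cement mold), the tantalum beads and the standard instruments in place of the present pair.
2. Reconcile the stated study term with the two-year schedule, so that the listed events are reported through the existing two-year visit for patients in follow-up.

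The cost is one IRB amendment and a small amount of extra event reporting. No new visit is needed, and neither the design nor the rules for excluding patients when the RTI is abandoned need to change.

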Use of Real Time Instrumentation (RTI) in Total Shoulder Arthroplasty: A Clinical Case Series

NCT01905241

01/10/2014

Use of Real Time Instrumentation (RTI) in Total Shoulder Arthroplasty: A Clinical Case Series

Principle Investigator

[name] [name]

Co Investigators

[name] MD

[name] DO

Study coordinator

[name]

Overall Summary

Glenoid component loosening is the most common complication of total shoulder arthroplasty. Loosening is associated with malposition of the implant as well as the quality of the glenoid bone. Past studies from our research group have addressed these problems by investigating novel surgical technologies to increase the accuracy of glenoid implant placement. Over the course of multiple IRB approved clinical trials, use of our preoperative planning software in combination with patient specific instrumentation (PSI) or intelligent reusable instrumentation (IRI) has proven to more accurately place the glenoid guide pin than conventional standard of care techniques.(Figure 1) (Figure 2)

Continuing our work, we propose a clinical case series to evaluate a new surgical instrumentation technique that combines the features of PSI with the IRI technology that we have termed Real Time Instrumentation (RTI). We will measure implant placement with RSA and 3D CT imaging. We will measure pre-operative bone quality using quantitative CT Scan to measure trabecular bone volume and correlate these findings with bone samples removed from the humeral head and measured by microCT and mechanical testing of the bone samples. This bone tissue is normally removed and discarded as part of the standard of care for preparation of the bone for placement of the humeral head component. We have performed all of the work required to define both the safety of all components of the proposed study in the completed PSI study and the ongoing IRI study. Since application to the IRB for study of the IRI technology Custom Orthopaedic Solutions (Cleveland Clinic NewCo) has received in April 2013 FDA approval for this technology.

Glenoid Instrumentation and Pre-operative planning

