Using the Smartbone surrogate model, the surgeon visually compares the exposed glenoid surface to the Smartbone model to ensure that the two match for size and shape. Any adjustments to the surgical site may be done by the surgeon to optimize the match between the model and the exposed glenoid surface. Prior to molding the bone cement, bone wax is wiped onto the model to ensure proper release of the cement mold. The surgeon will then mold bone cement around the pin in the Smartbone, capturing the trajectory of the pin and the unique contours of the glenoid rim. A small pin sleeve is inserted over the pin to be embedded within the cement model. Once the bone cement has cured, it is removed from the model and placed onto the patient's glenoid surface. The bone morphology captured in the mold aligns the mold to the patient's anatomy. When surgeon feels that the model has good fit of the glenoid surface, he may continue with pin placement. After placement of the guide pin, the RTI mold is removed and the remainder of the procedure is completed using the implant manufacturer's equipment and standard surgical protocols. Any adjustments in guide pin position can be performed by the surgeon based upon surgical judgment. The surgeon can make any change needed and use any means or instrument that would otherwise be used for standard of care surgery to place the guide pin in any position that the surgeon believed to be best for the patient. If the pin is changed without the use of the RTI then the patient will be excluded from this study and the reasons for failure of the RTI technology to provide accurate pin placement based upon the surgeon's sole determination of accuracy will be recorded and later analyzed as a failure to treat. These patients will not receive post-operative CT Scans as we would not be able to use the data.

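### The only IRB notification rule names the IRI, the device of another study, and not the RTI that all 20 patients are enrolled to receive

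*Combined protocol and SAP*

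**What the plan says.** The Adverse Events and Data Monitoring Committee (DMC) section states "A Data Monitoring Committee will not be used", relies on surgical standards of care to protect patients, and then gives the reporting rule: "The IRB will be notified in writing of any adverse clinical event related to the use of the IRI or the standard instrumentation". A list of example adverse events follows; it names no device.

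The study device is introduced under Glenoid Instrumentation and Pre-operative planning: "We are proposing the first in man use of this technology for placement of the glenoid component". Detailed Study Design sets enrolment at 20 patients, all in the RTI group.

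Patient Enrollment lists what differs from usual care: "The only change for the case series will be the type of surgical instruments used to place the glenoid guide pin", followed by "coring of the bone to obtain bone tissue, placement of the beads and post-operative CT scanning".

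Two places remove patients in whom the RTI is not used or not relied on. Patient Enrollment says that if the surgeon chooses not to use the technique "the patient would be excluded from the study without post-operative imaging". Detailed Study Design says: "If the pin is changed without the use of the RTI then the patient will be excluded from this study". In both cases the reasons are recorded and analysed, but neither place mentions reporting to the IRB.

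**The concern.** A notification rule works through its trigger. Here the trigger is an event's relation to one of two named things: the IRI, to which no patient in this study is enrolled, and the standard instrumentation. The bone cement mould made in theatre and placed on the glenoid is neither. The same is true of the beads pressed into the implant and injected into bone.

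Events related to a device on its first human use are those an IRB most needs to see. With no DMC, the protocol names no second recipient. Staff who apply the sentence literally would have no written duty to notify the IRB of an event attributed to the mould or the beads.

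**Working it through.** The plan gives no figure on this point and none is needed. The check is whether any text brings RTI-related events within the duty to notify.

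**1. Could IRI be shorthand for RTI?** No.
- Glenoid Instrumentation and Pre-operative planning describes the IRI as a tool with adjustable legs, studied under IRB #12-997. It describes the RTI as a mould of the bone model made in the operating room.
- Outcome Measures and Statistical Methods list them as separate groups to be compared.
- Data Sheets, just before the adverse event section, refers correctly to the RTI instruments.

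**2. Where might the wording come from?** The caption to Figure 2 describes IRB #12-997 as IRI against standard of care. The rule's pairing of IRI with standard instrumentation matches that comparison. The present study is a single-group case series. A carry-over is therefore the likely explanation, though this is inference.

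**3. Which events does the sentence reach as written?**

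| Event related to | Reached by the rule? |
|---|---|
| IRI | Yes, but no patient is enrolled to it |
| Standard instrumentation, including after RTI is abandoned | Yes |
| RTI mould | No |
| Tantalum beads | No |
| Bone coring | Not named |
| Post-operative CT | Not named |

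**4. Does other text fill the gap?** No other section contains an IRB notification rule. The list of adverse events says what counts as an event but does not widen the trigger. Recording the reasons for RTI failure serves refinement of the technology.

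**5. Would changing IRI to RTI be enough?** It would bring in the mould. The beads would remain outside, and the text would still not say whether the rule follows a patient who has been excluded from the study.

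**6. How many patients are affected?** All 20 planned. No human RTI experience is reported. The 60 patients cited without a technology-related complication were in the PSI and IRI studies. The beads have been placed in 22 IRI-study patients without a reported adverse event, so they are less novel than the mould, but the rule omits them equally.

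**The case against.** The strongest reply is that this is an obvious slip. Taken literally, the study-instrument half of the rule would apply to nobody enrolled here, so a sensible reader would substitute the RTI. Other safeguards exist too: the surgeon may revert to standard care at any time, the reasons for RTI failure are recorded, and a research assistant attends every operation and records the surgeon's comments. RTI problems would probably be noticed and written down.

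Much of that stands. It bears on how likely harm and non-reporting are, but it does not create a duty to notify, and a written safety rule should not depend on readers correcting it. Institutional policy might require reporting anyway, but the documents cite none.

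A reader might infer more than the documents support:

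- **That RTI-related harm will go unreported.** The text shows a gap in the rule. It does not show what staff would do. Nor can the gap be turned into a probability: the documents give no RTI event rate, and the chance that an event occurs is not the chance that it goes unreported.
- **That abandoned cases escape reporting altogether.** Standard instrumentation is already named, and the sentence does not require the patient to remain in the study. What is missing is an explicit statement for excluded patients, and cover for an event caused by the mould before it was abandoned.
- **That every departure from usual care was overlooked.** The rule does address instruments, under the wrong name. The humeral head tissue kept for testing is normally removed and discarded.
- **That the protocol conceals the lack of human RTI data.** The Overall Summary says "We have performed all of the work required to define both the safety of all components of the proposed study", which is too broad for the mould. But that is introductory narrative, and the next section discloses that the RTI evidence is pre-clinical and that human use is new. It is not a ground for this point.

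**Conclusion.** Wrong as written. The protocol's only IRB notification rule names a device from another study and omits the one under test, which has no reported prior human use. It also omits the study-specific beads. The gap applies to all 20 planned patients and concerns safety reporting only; the comparison of implant position with plan does not depend on it.

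The conclusion rests on the plain wording of the rule and on the absence of any other notification rule in the document. It needs no assumed event rate. That the wording is a carry-over is probable but not established. The correction is needed either way.

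**What to change.** Reword the sentence to require written IRB notification of any adverse clinical event related to the RTI, the standard instrumentation, or any other study-specific procedure (tantalum beads, bone coring, post-operative CT). State that this applies to every patient in whom RTI was attempted, including those later excluded under Patient Enrollment or Detailed Study Design.

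The cost is one sentence and possibly a few more IRB letters. No committee, extra scan or pause in enrolment is needed.
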